[figure not shown]
[figure not shown]
[figure not shown]
[figure not shown]
[figure not shown]
[figure not shown]
[figure not shown]
[figure not shown]
[figure not shown]
[figure not shown]
[figure not shown]

Clinical Study Protocol

Document Number:		c20065772-02
EudraCT No.: EU Trial No.:	NA	
BI Trial No.:	0352-2110	
BI Investigational Product(s):	NA	
Title:	A biomarker evaluation study in patients with geographic atrophy secondary to age-related macular degeneration (AMD) evaluating the use of microperimetry (fundus-controlled perimetry) and Swept Source-OCT in assessing changes in retinal sensitivity and anatomy over time.	
Lay Title:	Geographic Atrophy Biomarker Evaluation Study (GABiE)	
Clinical Phase:	0	
Trial Clinical Monitor:	 Phone  Fax 	
Coordinating Investigator:	 Tel:  ; Fax:  E-mail: 	
Status:	Final Protocol (Revised Protocol (based on global amendment No. 1))	
Version and Date:	Version: 2.0	Date: 21 Aug 2019
Page 1 of 31		
Proprietary confidential information. © 2019 Boehringer Ingelheim International GmbH or one or more of its affiliated companies. All rights reserved. This document may not - in full or in part - be passed on, reproduced, published or otherwise used without prior written permission.		

CLINICAL TRIAL PROTOCOL SYNOPSIS

Company name	Boehringer Ingelheim Pharma GmbH & Co.KG
Finished product name	NA
Active ingredient name:	NA
Protocol date	26 Jul 2018
Revision date	21 Aug 2019
Trial number	0352-2110
Title of trial:	A biomarker evaluation study in patients with geographic atrophy secondary to age-related macular degeneration (AMD) evaluating the use of microperimetry (fundus-controlled perimetry) and Swept Source-OCT in assessing changes in retinal sensitivity and anatomy over time.
Principal Investigator < for single-centre trial or > Coordinating Investigator< for multi- centre trial if applicable >:	 Tel:  ; Fax:  E-mail: 
Trial site(s):	Multi-center trial
Clinical phase:	0
Objective(s):	To investigate the use of microperimetry and SS-OCT in assessing the natural changes of retinal sensitivity and anatomy in the perilesional zone of geographic atrophy areas in patients with dry age-related macular degeneration.
Methodology:	Biomarker Evaluation Study
Number of patients entered:	50
Number of patients on each treatment:	NA
Diagnosis :	Geographic atrophy in patients with dry age-related macular degeneration.

Main in- and exclusion criteria	
Inclusion criteria:
 
 • Best Corrected Visual Acuity (BCVA) of 20/63 or better (Snellen equivalent) using ETDRS charts at starting distance of 4 m • Well demarcated area(s) of GA secondary to AMD with no evidence of prior or active choroidal neovascularization (CNV) • At least one patch of GA more than 0.5 disc area (DA) • Sufficiently clear ocular media, adequate pupillary dilation, and fixation to permit quality fundus imaging 
Exclusion Criteria:
 
 • GA in either eye due to causes other than AMD (for example, monogenetic macular dystrophies [e.g., Stargardt disease, cone rod dystrophy] or toxic maculopathies [e.g., chloroquine/hydroxychloroquine maculopathy]) • Receiving active treatment in any studies of investigational drugs for GA/dry AMD
Test product(s):	NA
dose:	NA
mode of administration:	NA
Comparator products:	NA
dose:	NA
mode of administration:	NA
Duration of observation:	12 months
Endpoints	
All of the following endpoints will be assessed for the study eye.
 
Primary:
 
 • Change from baseline in retinal sensitivity in the junctional zone and in the perilesional zone of the largest atrophic loci as assessed by microperimetry at week 12 • Change from baseline in RPE layers thickness in the junctional zone and in the perilesional zone as measured by SS-OCT at week 12 • Change from baseline in photoreceptor layer thickness in the junctional zone and in the perilesional zone as measured by SS-OCT at week 12 
Secondary:
 
 • Change from baseline in retinal sensitivity in the junctional zone and in the perilesional zone of the largest atrophic loci as assessed by microperimetry at week 24 and 48 • Change from baseline in RPE layer thickness in the junctional zone and in the perilesional zone as measured by SS-OCT at week 24 and 48

	
• Change from baseline in photoreceptor layer thickness in the junctional zone and in the perilesional zone as measured by SS-OCT at week 24 and 48• Change from baseline in the GA area as measured by FAF at week 12, 24 and 48• Change in BCVA score as assessed by ETDRS chart at a starting distance of 4 m at week 12, 24 and 48• Change in LLVA score as assessed by ETDRS chart under low luminance conditions at a starting distance of 4 m at week 12, 24 and 48• Number of scotomatous points assessed by microperimetry at week 12, 24 and 48• Change from baseline in the area of choroidal non-perfusion as measured via OCT-A at week 12, 24 and 48
Safety criteria:	Adverse events
Statistical methods:	All endpoints will be evaluated descriptively.

FLOW CHART

Trial Periods	Screening	Observation Period			
Visit	1	2 (Baseline)	3	4	5
Weeks	-4 to -1		12	24	48
Time window for visits			±2 weeks	±2 weeks	±2 weeks
Informed consent	X				
In/exclusion criteria	X	X			
Demographics	X				
Medical history	X				
BCVA testing (starting at 4 m)	X	X	X	X	X
Low Luminance Visual Acuity		X	X	X	X
SD-OCT	X	X	X	X	X
SS-OCT with OCT-A	X	X	X	X	X
FAF and Near Infrared imaging	X	X	X	X	X
Microperimetry	X ¹⁾	X	X	X	X
Concomitant medication	X	X	X	X	X
Concurrent ocular procedures	X	X	X	X	X

- 1) Microperimetry examination to be executed twice with few minutes of resting
- 2) Do be performed only after Microperimetry testing has been done in order to avoid that the microperimetry is influenced by the light used for Color Photography.
- 3) Optional

TABLE OF CONTENTS

TITLE PAGE	1
CLINICAL TRIAL PROTOCOL SYNOPSIS	2
FLOW CHART	5
TABLE OF CONTENTS	6
ABBREVIATIONS	9
1. INTRODUCTION.....	10
1.1 MEDICAL BACKGROUND.....	10
1.2 RATIONALE FOR PERFORMING THE STUDY	10
2. TRIAL OBJECTIVES AND ENDPOINTS.....	11
2.1 MAIN OBJECTIVES, PRIMARY AND SECONDARY ENDPOINTS.....	11
2.1.1 Main objectives.....	11
2.1.2 Primary endpoints.....	11
2.1.3 Secondary endpoints	11
2.2 FURTHER OBJECTIVES AND FURTHER ENDPOINTS	11
2.2.1 Further objectives	11
2.2.2 Further endpoints	12
3. DESCRIPTION OF DESIGN AND TRIAL POPULATION.....	13
3.1 OVERALL STUDY DESIGN AND PLAN	13
3.2 SELECTION OF STUDY POPULATION.....	13
3.2.1 Main diagnosis for study entry	13
3.2.2 Inclusion criteria	13
3.2.3 Exclusion criteria	14
3.2.4 Withdrawal of patients from study participation	15
3.2.4.1 Withdrawal of consent for study participation.....	15
3.2.4.2 Discontinuation of the study by the sponsor	15
4. TREATMENTS.....	16

11. DESCRIPTION OF GLOBAL AMENDMENT(S)		
30		
11.1	GLOBAL AMENDMENT 1	30

11.2 GLOBAL AMENDMENT 231

ABBREVIATIONS

AE	Adverse Event
AESI	Adverse Event of Special Interest
AMD	Age-related Macular Degeneration
BCVA	Best Corrected Visual Acuity
BI	Boehringer Ingelheim
CI	Confidence Interval
CNV	Choroidal Neovascularization
CRA	Clinical Research Associate
CRC	Central Reading Center
CRF	Case Report Form, paper or electronic (sometimes referred to as “eCRF”)
CTR	Clinical Trial Report
DA	Disc Area
eDC	Electronic Data Capture
ETDRS	Early Treatment Diabetic Retinopathy Scale
EudraCT	European Clinical Trials Database
FAF	Fundus Autofluorescence
FDA	Food and Drug Administration
GA	Geographic Atrophy
GCP	Good Clinical Practice
IEC	Independent Ethics Committee
IMP	Investigational Medical Product
IRB	Institutional Review Board
IReST	International Reading Speed Test
ISF	Investigator Site File
LLD	Low Luminance Deficit
LLVA	Low Luminance Visual Acuity
MedDRA	Medical Dictionary for Drug Regulatory Activities
NEI VFQ-14	National Eye Institute Visual Function Questionnaire-14
OCT-A	Optical Coherence Tomography Angiography
PGx	Pharmacogenetics
RPE	Retinal Pigment Epithelium
SAE	Serious Adverse Event
SD	Standard Deviation
SD-OCT	Spectral Domain – Optical Coherence Tomography
SS-OCT	Swept Source – Optical Coherence Tomography
TSAP	Trial Statistical Analysis Plan
WHO	World Health Organization
YAG	Yttrium Aluminum Garnet

1. INTRODUCTION

1.1 MEDICAL BACKGROUND

In the developed world, age-related macular degeneration (AMD) is the leading cause of blindness. AMD is a medical condition which may result in blurred or no vision in the center of the visual field. It preferentially affects the central vision, which is needed for reading, driving, recognizing people's faces and color vision. AMD is divided into dry and wet AMD. However, it is better to describe AMD as the early phase which is virtually asymptomatic, intermediate phase with mild visual loss, which can then develop into advanced phase defined as Geographic Atrophy (GA) and / or Neovascular (or wet) AMD leading to significant visual loss. Highlighting the complexity of the disease, in some patients who are first diagnosed to have wet AMD and be treated with anti-VEGF therapy, these patients can then develop GA even after the wet component is under control or stabilized.

The pathogenesis of AMD is not well understood although significant progress has been made in the past few years. Several theories have been put forward, including oxidative stress, mitochondrial dysfunction, choroidal perfusion dysfunction and inflammatory processes. The imbalance between production of damaged cellular components and degradation leads to the accumulation of intracellular lipofuscin and extracellular matrix material, commonly seen clinically as yellow deposit called drusen. Photoreceptor loss occurs overlying the drusen area. Incipient atrophy is demarcated by thinning or pigmentary changes of the Retinal Pigment Epithelium (RPE), the supporting layer of the photoreceptors in the macular area during early disease stages. The interaction between the photoreceptors / RPE and the underlying choroid (the blood supply to the retina) in the disease state is unclear. In the advanced stages of AMD, atrophy of the RPE over a geographic area and/or development of neovascularization result in massive loss of photoreceptors and central vision loss.

1.2 RATIONALE FOR PERFORMING THE STUDY

GA secondary to AMD is an indication with high unmet medical need. Decision making in early clinical trials may be based on quantification of changes in retinal sensitivity or anatomical changes such as thinning of the photoreceptor layer. Retinal sensitivity in a specific area of the retina can be measured by fundus-controlled perimetry (microperimetry). Anatomical changes of retinal or choroidal structures or the RPE can be analysed via OCT imaging, and correlated to changes in light sensitivity.

In order to be able to address future scientific questions, patients will be asked to voluntarily donate biospecimens for banking. If the patient agrees, banked samples may be used for future drug development projects, e.g. to identify patients that are more likely to benefit from a treatment or experience an adverse event (AE), and thereby better match patients with therapies.

2. TRIAL OBJECTIVES AND ENDPOINTS

2.1 MAIN OBJECTIVES, PRIMARY AND SECONDARY ENDPOINTS

2.1.1 Main objectives

The main objective of this study is to investigate the use of microperimetry and Swept Source – Optical Coherence Tomography (SS-OCT) in assessing the natural changes of retinal sensitivity and anatomy in the retina of patients with GA.

2.1.2 Primary endpoints

All of the following endpoints will be assessed for the study eye.

- Change from baseline in retinal sensitivity in the junctional zone and in the perilesional zone of the largest atrophic loci as assessed by microperimetry for the evaluation of macular functional response at week 12
- Change from baseline in RPE layer thickness in the junctional zone and in the perilesional zone as measured by SS-OCT at week 12
- Change from baseline in photoreceptor layer thickness in the junctional zone and in the perilesional zone as measured by SS-OCT at week 12

2.1.3 Secondary endpoints

[figure not shown]
All of the following endpoints will be assessed for the study eye.

- Change from baseline in retinal sensitivity in the junctional zone and in the perilesional zone of the largest atrophic loci as assessed by microperimetry at week 24 and 48
- Change from baseline in RPE layer thickness in the junctional zone and in the perilesional zone as measured by SS-OCT at week 24 and 48
- Change from baseline in photoreceptor layer thickness in the junctional zone and in the perilesional zone as measured by SS-OCT at week 24 and 48
- Change from baseline in the GA area as measured by Fundus Autofluorescence (FAF) at week 12, 24 and 48
- Change in Best Corrected Visual Acuity (BCVA) score as assessed by Early Treatment Diabetic Retinopathy Scale (ETDRS) chart at a starting distance of 4 m at week 12, 24 and 48
- Change in Low Luminance Visual Acuity (LLVA) score as assessed by ETDRS chart under low luminance conditions at a starting distance of 4 m at week 12, 24 and 48
- Number of scotomatous points assessed by microperimetry at week 12, 24 and 48
- Change from baseline in the area of choroidal non-perfusion as measured via Optical Coherence Tomography Angiography (OCT-A) at week 12, 24 and 48

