3.2.2 Inclusion criteria

1. Signed and dated written informed consent in accordance with ICH-GCP and local legislation prior to admission to the study
2. Age ≥ 60 years
3. Ability (including a sufficient general health status according to investigators judgement) and willingness to undertake all scheduled visits and assessments including predefined methodology and standards utilizing microperimetry

4. GA secondary to AMD with no evidence of prior or active choroidal neovascularization (CNV) in the study eye
5. GA lesion in the study eye must reside completely within the FAF imaging field (Field 2-30 degree image centered on the fovea)
6. BCVA of 20/63 or better (Snellen equivalent) using ETDRS charts at starting distance of 4 m in the study eye
7. Well demarcated area(s) of GA secondary to AMD with no evidence of prior or active CNV in the study eye
 - The total GA lesion size $\geq 1.2 \text{ mm}^2$ (approximately ≥ 0.5 disc area [DA]) and $\leq 17.78 \text{ mm}^2$ (approximately ≤ 7 DA) and must reside completely within the FAF imaging field (Field 2–30 degree image centered on the fovea)
 - If GA is multifocal, at least 1 focal lesion must be $\geq 1.2 \text{ mm}^2$ (approximately ≥ 0.5 DA)
8. Sufficiently clear ocular media, adequate pupillary dilation, and fixation to permit quality fundus imaging in the study eye

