FAF is an imaging technology for the morphological assessment of GA. The fluorescence signal predominantly originates from fluorescent material within RPE cells. In eyes with GA, distinctly dark areas are observed where the atrophy of RPE cells leaves an absence of fluorescent signal allowing for a quantification of the size of atrophic regions. Furthermore, FAF may support the prediction of the progression rate of GA via imaging the appearance of the hyperfluorescent junctional zone (i.e., the boundary between dead and surviving RPE regions, which is likely to represent RPE and/or photoreceptor cells which are more likely to become atrophic). Specifically, retinæ with junctional zones of the banded or diffuse type are more likely to progress than retinæ with focal junctional zones. Therefore, the type of the junctional zone appearance in the FAF can be utilized to define inclusion criteria for this clinical study.

Low Luminance Visual Acuity (LLVA)

To determine visual acuity under low luminance condition, the amount of light transmitted is reduced by neutral density filters placed over the eye to be tested, and the subject is asked to read the letters of a ETDRS visual acuity chart which normally illuminated. Because of the filter-reduced luminance, LLVA scores are lower than for BCVA (the magnitude of the difference between BCVA and LLVA is defined as Low Luminance Deficit (LLD)). LLVA measurements reveal visual function abnormalities not apparent by measuring standard BCVA alone and might be a more sensitive indicator for the risk of visual decline than assessing only standard BCVA.

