7.3.1 Primary endpoint analyses

For each primary endpoint (see [section 2.1.2](#)), baseline is defined as the measurement obtained at Visit 2.

The following descriptive statistics will be calculated for the measurements related to the primary endpoints at each time point, as well as for the changes from baseline: N, arithmetic mean, Standard Deviation (SD), minimum, median, maximum, percentiles, arithmetic coefficient of variation.

Correlations (both Pearson and rank-based) of the changes from baseline of retinal sensitivity in the junctional zone and in the perilesional zone, respectively, of the largest atrophic loci as measured by microperimetry to the following endpoints will be estimated:

- Change from baseline in RPE layer thickness in the junctional zone and in the perilesional zone, respectively, as measured by SS-OCT and by SD-OCT
- Change from baseline in photoreceptor layer thickness in the junctional zone and in the perilesional zone, respectively, as measured by SS-OCT and by SD-OCT
- Changes from baseline in GA area as measured by FAF
- Change from baseline in the area of choriocapillaris flow deficits as measured via OCT-A at week 12, 24 and 48

Individual data as well as summary statistics will be visualised in respective graphical presentations, e.g. scatter plots or box-plots.

Correlations between the primary endpoints and continuous baseline characteristics will be investigated if necessary.

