7.3.2 Secondary endpoint analyses

The secondary endpoints (see [Section 2.1.3](#)) will be analysed descriptively.

Correlations between the secondary endpoints and continuous baseline characteristics will be investigated if necessary.

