11. DESCRIPTION OF GLOBAL AMENDMENT(S)

11.1 GLOBAL AMENDMENT 1

Date of amendment		21 Aug 2019
EudraCT number EU number		NA
BI Trial number		0352-2110
BI Investigational Product(s)		NA
Title of protocol		A biomarker evaluation study in patients with geographic atrophy secondary to age-related macular degeneration (AMD) evaluating the use of microperimetry (fundus-controlled perimetry) and Swept Source-OCT in assessing changes in retinal sensitivity and anatomy over time.
To be implemented only after approval of the IRB / IEC / Competent Authorities		
To be implemented immediately in order to eliminate hazard – IRB / IEC / Competent Authority to be notified of change with request for approval		
Can be implemented without IRB / IEC / Competent Authority approval as changes involve logistical or administrative aspects only		X

Section to be changed		3.3.2. Inclusion criterion #7
Description of change		
Well demarcated area(s) of GA secondary to AMD with no evidence of prior or active CNV in the study eye
 
 ○ The total GA lesion size $\geq 2.54 \text{ mm}^2$ (approximately ≥ 1 disc area [DA]) and $\leq 17.78 \text{ mm}^2$ (approximately ≤ 7 DA) and must reside completely within the FAF imaging field (Field 2–30 degree image centered on the fovea) ○ If GA is multifocal, at least 1 focal lesion must be $\geq 0.5 \text{ mm}^2$ (approximately ≥ 1 DA) 
was changed to
 
Well demarcated area(s) of GA secondary to AMD with no evidence of prior or active CNV in the study eye
 
 ○ The total GA lesion size $\geq 1.2 \text{ mm}^2$

		(approximately ≥ 0.5 disc area [DA]) and $\leq 17.78 \text{ mm}^2$ (approximately ≤ 7 DA) and must reside completely within the FAF imaging field (Field 2–30 degree image centered on the fovea) 
 ○ If GA is multifocal, at least 1 focal lesion must be $\geq 1.2 \text{ mm}^2$ (approximately ≥ 0.5 DA)
Rationale for change		A typographical error was erased and GA lesion size for inclusion was changed in order to resemble the later phase study population
Section to be changed		3.3.3. Exclusion criteria #2, 8
Description of change		Criteria were clarified to be applicable to the study eye only
Rationale for change		Clarification
Section to be changed		7.4
Description of change		The process for the use of study data for internal decision making was clarified
Rationale for change		Clarification

[figure not shown]
[figure not shown]

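### GA growth is correlated with retinal sensitivity on the raw area scale, with no stated allowance for a nearly 15-fold range of baseline lesion size

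*Combined protocol and SAP*

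**What the plan says.** - **Endpoint.** Section 2.1.3 lists "Change from baseline in the GA area as measured by Fundus Autofluorescence (FAF) at week 12, 24 and 48" as a secondary endpoint. No transformation is given. The unit mm² appears in the eligibility criterion, not in the endpoint.
- **Correlation.** Section 7.3.1 plans Pearson and rank correlations of the change in retinal sensitivity, in the junctional and perilesional zones, with four kinds of measure. One is "Changes from baseline in GA area as measured by FAF".
- **Lesion size.** Criterion 7 in section 3.2.2 sets limits on "The total GA lesion size": 1.2 to 17.78 mm². Multifocal GA is allowed. Section 11.1 records that the lower limit was 2.54 mm² before Global Amendment 1, and gives the reason: "GA lesion size for inclusion was changed in order to resemble the later phase study population".
- **Baseline size.** The nearest provision is in section 7.3.2: "Correlations between the secondary endpoints and continuous baseline characteristics will be investigated if necessary". Section 7.3.1 has a matching sentence for the primary endpoints. Both are conditional, and neither names baseline GA area.
- **Where atrophy spreads.** Section 5.2 describes the junctional zone as "the boundary between dead and surviving RPE regions" and says that cells there are the more likely to be lost next.
- **Status.** Section 7.2 makes every analysis exploratory. Sections 2.2.2 and 7.3.3 (further endpoints) are blank in this copy. The TSAP named in section 7.3 is not shown.

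**The concern.** If a lesion enlarges by movement of its border, two eyes with the same border speed gain different areas because their borders differ in length. Over a wide range of entry sizes, raw area change then mixes two things: how fast the border moves, and how large the lesion was at entry.

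This matters most for the correlation in section 7.3.1. Sensitivity is measured in the zones around the lesion, so border advance is its natural anatomical counterpart. Variation in baseline size would act as noise and pull the correlation toward zero, and the link between microperimetry and GA growth could be understated. Mean growth in mm² would also depend on the sizes enrolled, which affects how it carries over to another population.

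**Working it through.** **The plan's own figure.** The plan gives no figure for GA growth. Its only calculation, Table 7.5: 1, concerns retinal sensitivity. Taking the smallest n with P(χ²[n−1] ≤ n(n−1)w²/(t²·SD²)) ≥ 0.90, where t is the 0.975 quantile on n−1 degrees of freedom, reproduces all 12 cells. One of these is 47 patients at half-width w = 0.3 dB and SD 0.9. That calculation is untouched by this point.

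**Size range, from sections 3.2.2 and 11.1.**
- Current: 17.78/1.2 = 14.8-fold.
- Before Amendment 1: 17.78/2.54 = 7.0-fold.

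**Geometry, one round lesion of area A₀ whose border advances by g.**
- Area change = 2√(πA₀)·g + πg².
- Change in square-root area = √π·g, which does not depend on A₀.
- To first order, largest against smallest lesion: √14.8 = 3.85 now, √7.0 = 2.65 before.
- With g = 0.1 mm (assumed): 0.42 mm² at 1.2 mm² and 1.53 mm² at 17.78 mm², a ratio of about 3.6. The square-root change is 0.177 mm in both. For g from 0.05 to 0.20 mm the ratio is 3.5 to 3.7.

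**Simulation.** None of these inputs is in the documents: baseline area log-uniform over 1.2 to 17.78 mm²; border advance gamma-distributed with mean 0.15 mm/year and CV 0.3 to 0.7, independent of size; function correlated -0.50 with border advance. Single round lesions, no reading error:

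| Quantity | Raw area change | Square-root change |
|---|---|---|
| Correlation with baseline area | 0.40 to 0.72 | 0.00 |
| Pearson correlation with function (true -0.50) | -0.32 to -0.43 | -0.50 |
| Rank correlation with function | -0.30 to -0.41 | -0.45 to -0.47 |

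Rank correlation therefore does not remove the size component. With uniform or square-root-uniform sizes the raw Pearson correlation is -0.34 to -0.46. Partialling the raw correlation for baseline area gives -0.46 to -0.49 across these settings.

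**Relaxing the assumptions.**
- *Several foci.* For k equal round foci, area change = 2√(πkA₀)·g + kπg². With 1 to 5 foci, the correlation with function is -0.29 to -0.41 raw and -0.37 to -0.46 on the square-root scale. At 8 mm² and g = 0.1 mm, the square-root change is 0.18 mm for one focus and 0.35 mm for four, so that scale still depends on the number of foci.
- *Reading error at week 12, single lesions.* At 0.1 mm² per reading the scales are about equal (-0.22 to -0.37 raw, -0.22 to -0.38 square-root). At 0.2 to 0.3 mm² raw is slightly better (-0.10 to -0.27 against -0.08 to -0.25).
- *Partialling for square-root baseline area.* This equalled or beat the raw correlation in every scenario above in which function follows border advance.

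**Mean growth.** At the same border speed, lowering the limit from 2.54 to 1.2 mm² reduces mean raw growth by 13% (log-uniform sizes), 8% (square-root-uniform) or 4% (uniform).

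**The case against.** Much of the case on the other side is sound.

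- **The dilution follows from the assumed model.** Function was tied to border advance, so the scale proportional to border advance recovers it. If function is tied to area lost, the result reverses: -0.50 raw and -0.32 to -0.43 on the square-root scale. The documents do not settle which holds. Measuring sensitivity around the lesion makes a link to border advance the more natural reading, but does not establish it. This is a reason to show both scales.
- **The dilution is within sampling error.** With 50 patients and r = -0.50, the 95% CI by Fisher's z is tanh(-0.549 ± 1.96/√47), or -0.68 to -0.26. The diluted values lie inside it. That stands, but a systematic shift is still worth removing when doing so is nearly free.
- **Mean area growth is a legitimate description.** The size limits were meant to match a later-phase population, so dependence of the mean on the sizes enrolled is not an error in itself. That stands.
- **Baseline correlations are already allowed.** They are, if judged necessary. They could show that growth depends on size, but would leave the section 7.3.1 correlation unadjusted.

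A reader might infer that growth is analysed only in raw area. This copy cannot show that: the further-endpoint sections are blank and the TSAP is not shown. A reader might also infer that Amendment 1 created the problem, but the range was already 7-fold.

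**Conclusion.** The point holds as a modest improvement to an exploratory analysis. In the visible text, GA growth is defined and correlated on the untransformed area scale across a 14.8-fold range of entry sizes, with no firm provision for baseline size.

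The direction follows from border-driven growth, which section 5.2 makes plausible. The size does not come from the documents. The drop from -0.50 to between -0.32 and -0.43 needs single round lesions, no reading error, and function that follows border advance. With multifocal lesions the square-root gain is smaller, and at week 12 it can vanish with reading error of about 0.2 mm².

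A reader might go further and treat this correlation as a core output, or conclude that raw area should be replaced. The documents support neither. The main objective concerns microperimetry and SS-OCT, GA area is a secondary endpoint and one of four kinds of correlate, and replacing raw area would be a trade-off. No hypothesis test, sample size or primary endpoint is affected.

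**What to change.** Keep raw change in GA area (mm²) as the stated secondary endpoint. In sections 7.3.1 and 7.3.2, or in the TSAP:

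1. Prespecify change in square-root GA area (mm) at weeks 12, 24 and 48 as a supplementary scale.
2. Report the correlations of sensitivity change with GA growth on the raw scale, on the square-root scale, and partialled for square-root baseline GA area.
3. Describe baseline GA area and number of foci alongside the growth results.

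If the TSAP already contains these, a cross-reference in section 7.3.1 is enough.

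Cost: a short paragraph and a few extra tables. Baseline area is already assessed for eligibility, and the number of foci can be read from the same images. The downsides are that a change in mm is harder to read clinically than one in mm², and that the correction is only approximate for multifocal lesions.
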